**Figure 2. Adverse Event Collection**

### 6.1.5 Adverse Event Reporting

In the event of a SAE, whether associated with study drug or not, the Investigator will notify Clinical Pharmacovigilance within 24 hours of the site being made aware of the SAE by entering the SAE data into the electronic data capture (EDC) system. For SAEs that occur prior to the site having access to the RAVE® system or if RAVE is not operable, the forms should be faxed or emailed to Clinical Pharmacovigilance within 24 hours of the site being made aware of the SAE.

**[contact]**

The sponsor will be responsible for Suspected Unexpected Serious Adverse Reactions (SUSAR) reporting for the Investigational Medicinal Product (IMP) in accordance with Directive 2001/20/EC. The reference document used for SUSAR reporting in the EU countries will be the most current version of the Investigator's Brochure.

#### **6.1.6 Pregnancy**

Subjects and their partners should avoid pregnancy and males should avoid sperm donation throughout the course of the study, which is defined as from Study Day 1 until 30 days after the last dose of study drug if subjects do not take RBV, or from Study Day 1 until 6 months for WOCBP and 9 months for males after the last dose of the study drug containing RBV (or per local RBV label).

Pregnancy in a study subject must be reported to the AbbVie within 1 working day of the site becoming aware of the pregnancy. Subjects who report a positive pregnancy test during the Treatment Period must be notified to stop RBV (if applicable) immediately. Administration of DAAs may be continued at the investigator's discretion after discussion with the subject, if the benefit of continuing therapy is felt to outweigh the potential risk (as allowed per local guidance) (Section 5.4.1).

Information regarding a pregnancy occurrence in a study subject and the outcome of the pregnancy will be collected for pregnancies occurring up to 30 days after the end of treatment with DAAs only, or through Post-Treatment Week 28 (or per local RBV label) after the last dose of RBV for treatment with DAAs plus RBV. The investigator is encouraged to report the pregnancy information to the voluntary RBV Pregnancy Registry, if RBV is included within the regimen.

Subjects who discontinue study medications due to pregnancy will be monitored for SVR in the Post-Treatment Period as described in Section 5.4.1.

Pregnancy in a study subject is not considered an adverse event. However, the medical outcome of an elective or spontaneous abortion, stillbirth or congenital anomaly is considered a serious adverse event and must be reported to the Sponsor within 24 hours of the site becoming aware of the event.

### **6.1.7 Toxicity Management**

For the purpose of medical management, all adverse events and laboratory abnormalities that occur during the study must be evaluated by the investigator. All adverse events and laboratory abnormalities will be managed and followed to a satisfactory clinical resolution. The table of clinical toxicity grades "National Cancer Institute Common Terminology Criteria for Adverse Events, Version 4" is to be used in the grading of adverse events and laboratory abnormalities which is available on the Cancer Therapy Evaluation Program (CTEP) website at:  
[http://evs.nci.nih.gov/ftp1/CTCAE/CTCAE\\_4.03\\_2010-06-14\\_QuickReference\\_5x7.pdf](http://evs.nci.nih.gov/ftp1/CTCAE/CTCAE_4.03_2010-06-14_QuickReference_5x7.pdf).

A drug-related toxicity is an adverse event or laboratory value outside of the reference range that is judged by the investigator or the Sponsor as having a "reasonable possibility" of being related to the study drug (Section 6.1.3). A toxicity is deemed "clinically significant" based on the medical judgment of the investigator. Laboratory abnormalities will be managed as deemed clinically appropriate by the investigator until satisfactory resolution.

Investigators should avoid interrupting study drugs for more than 7 consecutive days. The Investigator should ensure that any study drug interruptions or RBV (if applicable) dose modifications and associated adverse events are promptly entered into the appropriate eCRFs.

The toxicity management guidelines below should be followed throughout the Treatment Period of the study.

#### **6.1.7.1                    Grade 1 or 2 Laboratory Abnormalities and Mild or Moderate Adverse Events**

Subjects who develop a mild or moderate adverse event or Grade 1 or 2 laboratory abnormality, other than those discussed separately in Section 6.1.7.4 (Management of Decreases in Hemoglobin) for subjects receiving RBV, Section 6.1.7.5 (Management of ALT Elevations), and Section 6.1.7.6 (Creatinine Clearance) may continue study drugs with follow-up per study protocol and in accordance with local standard of care.

#### **6.1.7.2                    Grade 3 or 4 Laboratory Abnormalities**

With the exception of Grade 3 or higher abnormalities of total bilirubin, uric acid, phosphorus, total cholesterol, triglycerides, or glucose (in subjects with a history of diabetes), if a subject experiences a Grade 3 or greater abnormal laboratory parameter during the Treatment Period, the abnormal laboratory test should be repeated. If the Grade 3 or greater abnormality is confirmed, the investigator should assess whether the abnormality can be managed medically without interruption of study drug, or whether study drugs should be interrupted and the laboratory parameter followed until it improves.

If study drugs are interrupted and restarted and the abnormality recurs, then study drugs should be permanently discontinued.

Decreases in serum hemoglobin or in calculated creatinine clearance or elevations of serum ALT should be managed according to the guidance in Section 6.1.7.4, Section 6.1.7.5, and Section 6.1.7.6 below. Grade 3 or greater abnormalities of total bilirubin, uric acid, phosphorus, total cholesterol, triglycerides or glucose (in subjects with a history of diabetes) should be managed medically as appropriate and do not require confirmation or study drug interruption unless deemed necessary by the investigator.

### **6.1.7.3 Severe Adverse Events or Serious Adverse Events**

If a subject experiences a severe adverse event (Grade 3+) or a serious adverse event that the investigator considers to have a reasonable possibility of relationship to study drug, the investigator should assess whether the adverse event can be managed medically without interruption of study drug, or whether study drugs should be interrupted until the event improves. If study drugs are interrupted and restarted and the adverse event recurs, then study drugs should be permanently discontinued.

If a subject experiences a severe adverse event (Grade 3+) or serious adverse event that is considered unrelated (no reasonable possibility) to the study drugs, it is not necessary to interrupt study drugs unless an interruption is required because of the nature of the event (e.g., unable to take oral medications).

The investigator should ensure that all serious adverse events are reported to AbbVie within 24 hours of awareness. Serious adverse event follow-up information, including associated dose interruptions (or discontinuations), must be reported to AbbVie within 24 hours of awareness by entering updated SAE information into the appropriate eCRFs.

Severe adverse events and any associated dose interruptions (or discontinuations) should be entered into the appropriate eCRFs.

#### **6.1.7.4 Management of Decreases in Hemoglobin**

##### **For subjects not receiving ribavirin:**

Hemoglobin decreases should be managed according to grade based on the guidance in Section 6.1.7.1 and Section 6.1.7.2 above.

##### **For subjects receiving ribavirin:**

Decreases in hemoglobin are a well characterized side effect of ribavirin exposure. If a subject receiving the standard dose of RBV experiences a hemoglobin decrease meeting one of the criteria outlined in Table 12, a confirmatory test should be performed. If the hemoglobin decrease is confirmed, the management guidelines in Table 12 should be followed. Management will be different for subjects without a history of known cardiac disease and subjects with known cardiac disease. Subjects experiencing decreases in hemoglobin that do not meet the criteria outlined in Table 12 may need hemoglobin evaluations at more frequent intervals at the discretion of the investigator.

In subjects with creatinine clearance less than 50 mL/min, RBV should be interrupted if subject experiences a confirmed decrease in hemoglobin to less than 10 g/dL. In these subjects, decreases in hemoglobin should be managed at the discretion of the investigator and as medically appropriate.

Use of hematologic growth factors (such as erythropoietin or filgrastim) or blood transfusions are permitted at the discretion of the investigator. Management of hematologic growth factor therapy is the responsibility of the Investigator, and growth factors will not be provided by AbbVie.

Alternate management of hemoglobin decreases outside of these criteria is permitted with approval of the AbbVie Therapeutic Area Medical Director.

**Table 12. Ribavirin Dose Modification Guidelines in Management of Hemoglobin Decreases**

Subjects with Creatinine Clearance $\geq$ 50 mL/min		
	Reduce RBV Daily Dose a if:	Interrupt RBV b if:
Hemoglobin in Patients with No Cardiac Disease	< 10 g/dL	< 8.5 g/dL
Hemoglobin in Patients with History of Stable Cardiac Disease	$\geq$ 2 g/dL decrease in hemoglobin during any 4 week treatment period (permanent dose reduction)	< 12 g/dL despite 4 weeks at reduced RBV dose

- a. Reduce RBV daily dose in accordance with local RBV prescribing information/product label or per the discretion of the investigator.
- b. If the abnormality is reversed, RBV may be restarted at the discretion of the investigator and in accordance with local RBV prescribing information/product label.

#### 6.1.7.5 Management of ALT Elevations

Transient asymptomatic grades 3 – 4 ALT elevations have been observed in approximately 1% of subjects receiving paritaprevir/r-containing regimens. If a subject experiences a post-baseline increase in ALT to  $> 5 \times$  ULN that is increased from the previous measurement, the subject should have a confirmatory ALT measurement performed.

If the ALT increase is confirmed to be  $> 5 \times$  ULN and increased from the previous measurement, the recommendations below should be followed:

- Evaluate for alternative etiology of ALT elevation: update medical history and concomitant medications eCRF (if applicable), and obtain additional testing as appropriate.
- Manage the subject as medically appropriate.
- Repeat ALT, AST, total and fractionated bilirubin, alkaline phosphatase and INR within 1 week. Repeat liver chemistries as indicated until resolution.
- Consider discontinuing study drugs if ALT level is persistently  $> 10 \times$  ULN.
- Discontinue study drugs if the following is observed at any time:

- Increasing direct bilirubin, increasing INR, or onset of symptoms/signs of hepatitis.

Alternate management of ALT increases is permitted with approval of the AbbVie Therapeutic Area Medical Director.

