### **Hepatic Decompensation**

In late 2015, several cases of hepatic decompensation were reported in patients treated post-marketing with 2D or 3D with or without RBV, some of which resulted in fatalities or necessitated liver transplants. These occurrences were observed in patients who already had advanced or decompensated cirrhosis prior to starting treatment. Although complete information on baseline clinical status and laboratory values was infrequently available, patients with severe outcomes of death or liver transplantation generally had evidence of more advanced cirrhosis and portal hypertension. Laboratory findings (when available) associated with events of hepatic decompensation and hepatic failure were characterized by the acute onset of rising direct serum bilirubin levels with additional clinical signs and symptoms of hepatic decompensation, typically without associated ALT elevations. The label was subsequently updated to contraindicate 3D and 2D in patients with decompensated cirrhosis (i.e., CPB or CPC). The current study is intended to evaluate the pharmacokinetics, safety, efficacy and the long-term outcomes of ombitasvir, paritaprevir, ritonavir with or without dasabuvir and with or without ribavirin in pediatric subjects with genotype 1 or 4 chronic hepatitis C with or without compensated cirrhosis. Subjects with current evidence or a prior history of liver decompensation are excluded from this study.

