### **3.2 Benefits and Risks**

Part 1 of this study is a Phase 2 study in which eligible HCV GT1-infected pediatric subjects will receive OBV, PTV, RTV and DSV with or without RBV for 12 weeks. Part 2 of this study is a Phase 3 study in which eligible genotype 1 or 4-infected subjects will receive OBV/PTV/RTV with or without DSV and with or without RBV for 12 or 24 weeks depending on HCV genotype, sub-genotype and cirrhosis status. OBV/PTV/RTV and DSV with or without RBV was evaluated in > 2300 adult subjects with HCV GT1 infection in six Phase 3 studies. OBV/PTV/RTV and DSV with or without RBV achieved SVR12 greater than 97% overall in HCV GT1-infected subjects, including those with compensated cirrhosis, with the label recommended regimens. OBV/PTV/RTV with or without RBV was evaluated in 135 adult subjects with HCV GT4 infection in a Phase 2 study. Similarly high SVR12 rates (100%) were observed in this study with OBV/PTV/RTV with RBV.

OBV/PTV/RTV and DSV with or without RBV was well tolerated in the Phase 3 studies in genotype 1-infected adults with discontinuation due to AEs approximately 1%. Adverse events that are known and those not previously described, may occur as detailed in the informed consent and assent for this study. In addition, subjects may experience inconvenience or discomfort related to the study visits or study procedures.

Post-marketing cases of hepatic decompensation were reported in patients treated with OBV/PTV/RTV with or without DSV with or without RBV, some of which resulted in fatalities or necessitated liver transplants. These occurrences were observed in patients who already had highly advanced or decompensated cirrhosis prior to starting treatment. In this study, patients with a history of or existing decompensation will not be included in the study. Other risks associated with OBV/PTV/RTV with or without DSV and with or

without RBV include the risks of toxicity and virologic failure. Adverse events associated with treatment have been limited and manageable based on the results from the Phase 2/3 studies. Given the potential high rate of cure in HCV GT1 and GT4-infected subjects, the risk-benefit profile is favorable.

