### **Child-Pugh Score and Category**

The Child-Pugh score will be calculated and documented prior to Day 1 Visit for cirrhotic subjects only. Subjects who were considered to be non-cirrhotic at the screening visit but identified as cirrhotic (according to definitions listed here) during the screening process will return to the site prior to the baseline visit for Child-Pugh assessment.

The Child-Pugh score uses five clinical measures of liver disease (3 laboratory parameters and 2 clinical assessments). Child-Pugh score will be determined at the screening visit as indicated in [Appendix C](#). The Child-Pugh score will be automatically calculated prior to Day 1 by EDC RAVE once the investigator or designated site personnel enters the subject's parameters (as listed in [Table 9](#)). A total score of 5 – 6 is considered Class A (compensated disease); 7 – 9 is Class B (significant functional compromise); and 10 – 15 is Class C (decompensated disease).

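### For a subject with cirrhosis, the protocol specifies no repeat test, interruption or stop when direct bilirubin rises without an ALT elevation

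*Protocol*

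**What the plan says.** Protocol Section 6.1.7.5 (Management of ALT Elevations) asks for a confirmatory ALT when the value passes 5 x ULN. Once ALT is confirmed above five times "ULN and increased from the previous measurement, the recommendations below should be followed". The last item on that list is an instruction to discontinue for any of these: "Increasing direct bilirubin, increasing INR, or onset of symptoms/signs of hepatitis".

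Outside that list, two sections deal with bilirubin by grade. Under Section 6.1.7.1, subjects with Grade 1 or 2 laboratory abnormalities "may continue study drugs with follow-up per study protocol and in accordance with local standard of care". Under Section 6.1.7.2, Grade 3 or higher abnormalities are repeated and assessed, but total bilirubin is among the named exceptions. Those exceptions "should be managed medically as appropriate and do not require confirmation or study drug interruption unless deemed necessary by the investigator".

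Section 3.0 (Hepatic Decompensation) reports post-marketing cases, some fatal or leading to transplant. Where laboratory data were available they showed "acute onset of rising direct serum bilirubin levels with additional clinical signs and symptoms of hepatic decompensation, typically without associated ALT elevations". It adds: "The label was subsequently updated to contraindicate 3D and 2D in patients with decompensated cirrhosis". Part 2 enrolls 12- to 17-year-olds with or without compensated cirrhosis, and SAP Section 11.2.1.1 lists hepatic decompensation and hepatic failure as an adverse event of special interest.

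**The concern.** The only stop rule that names direct bilirubin depends on a marked ALT rise. The protocol's own account of the serious hepatic cases says that an ALT rise is typically absent. The bilirubin exemption in Section 6.1.7.2 makes sense for the rise expected with this regimen, which Section 3.0 describes as mainly indirect and due to transporter inhibition and ribavirin hemolysis. As written, though, it also covers a predominantly direct rise, which has a different meaning in a subject with cirrhosis.

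What is at stake is delay in a few subjects with a potentially severe outcome. From Week 4 onward scheduled treatment visits are four weeks apart, so without a specified repeat the next planned measurement may be four weeks away.

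**Working it through.** No figure in the plan bears on this rule, so the main check is to take one case through every section that could apply. The case is a subject with compensated cirrhosis on treatment, with ALT not elevated and total bilirubin rising mainly in the direct fraction.

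1. **Section 6.1.7.5.** The entry condition, confirmed ALT above 5 x ULN and increasing, is not met. The stop item says it applies at any time, but it is an item in a list governed by that condition, in a section about ALT.
2. **Section 6.1.7.1.** SAP Table 10, which follows CTCAE version 4, puts total bilirubin above 1.5 and up to 3 x ULN in Grade 2. At, say, 2.5 x ULN the subject may continue with ordinary follow-up.
3. **Section 6.1.7.2.** Above 3 x ULN the value is Grade 3 and falls under the named exemption. Direct bilirubin is not mentioned, and the documents give no grade for it, so this section supplies no usable trigger. Grade 3 or higher INR is not exempt and would be repeated whatever the ALT.
4. **Section 6.1.7.3.** This applies to severe or serious adverse events. If the event is judged related, the investigator assesses whether to interrupt, and stops permanently if it recurs on restart. Under Section 6.1.1.1 a laboratory change alone is not automatically an adverse event.
5. **Section 6.1.7, opening.** The investigator has to assess every laboratory abnormality and follow it until it resolves satisfactorily. No test, interval or action is named.
6. **Section 5.1.2.** Unscheduled safety visits are allowed if the investigator sees a need.
7. **SAP Section 11.3.2.** Total bilirubin at or above 2 x ULN and above baseline is counted whatever the ALT. A direct:total ratio above 0.4 is used only together with ALT above 3 x ULN. These are summaries for reporting, not actions for a subject.

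Steps 1 to 3 specify no action for the isolated direct rise. Steps 4 to 6 leave the response to judgment.

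**Number of subjects (illustration).** Section 3.0 gives pediatric cirrhosis as below 2% in some series and up to 8% in a referral series that it says probably overstates advanced disease. Assume that 1%, 2% or 8% applies to the 26 Part 2 subjects:

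- 26 x 0.01 = 0.26
- 26 x 0.02 = 0.52
- 26 x 0.08 = 2.08

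Section 3.0 also gives 15% of adults on 3D + RBV reaching bilirubin of at least 2 x ULN. If that applied to these subjects:

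- 0.26 x 0.15 = 0.04
- 0.52 x 0.15 = 0.08
- 2.08 x 0.15 = 0.31

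These counts come before setting aside the mainly indirect rises. Section 5.5.3 sets no quota or cap on cirrhosis, so the true number could differ.

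**Efficacy cost of one early stop.** 1/62 = 1.6 percentage points. With the Wilson interval of SAP Section 10.3.2, a change from 56/62 to 55/62 moves the lower 95% bound from 80.5% to 78.5%. The criterion is 67%.

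**The case against.** The strongest reply is that the protocol does not leave such a subject unattended. The investigator must evaluate and follow every abnormality, may recall the subject early, and may stop drug at any time under Section 5.4.1. The post-marketing pattern also included clinical signs. A subject with such signs has an adverse event, and if it is severe or serious and judged related, Section 6.1.7.3 directs an interruption decision whatever the ALT. All of this stands. A reader might infer that no response of any kind is required, and the documents do not support that. What is missing is a specified test, interruption or stop, of the sort the protocol gives for ALT and hemoglobin.

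The second reply is population. Section 3.2 says the cases already had "highly advanced or decompensated cirrhosis prior to starting treatment". Section 5.2.2 excludes current or past Child-Pugh B or C, prior decompensation, albumin below 2.8 g/dL and bilirubin above 3.0 mg/dL. In adults with compensated cirrhosis, 2% per arm stopped for adverse events in the 380-subject 3D + RBV study, and none of 60 did on 3D alone. This makes the event unlikely but does not remove it. Section 3.0 links the worst outcomes to more advanced cirrhosis and portal hypertension. No criterion excludes portal hypertension, and platelets down to 25,000 per mm3 are allowed.

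A reader might also infer that crossing 3 mg/dL shows decompensation, because it adds two Child-Pugh points and could move a subject from Class A to Class B. The documents do not support this inference. The score uses total bilirubin, which the regimen is expected to raise through the indirect fraction. In this protocol it is also an entry assessment: "The Child-Pugh score will be calculated and documented prior to Day 1 Visit for cirrhotic subjects only".

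**Conclusion.** The gap is real but narrow. For a predominantly direct bilirubin rise without ALT elevation in a subject with cirrhosis, no confirmatory test, interruption or stop is specified, and the Section 6.1.7.2 exemption can be read as covering that rise. It is a gap in the action rule, not in data collection. Direct bilirubin is in the chemistry panel (Table 8), and Appendix C requires coagulation tests at all treatment visits in cirrhotic subjects.

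No decompensation rate is given, so expected events cannot be stated. Under the assumed cirrhosis rates the rule concerns about 0.3 to 2.1 subjects, and the case rests on severity rather than frequency. A mandatory stop at a direct:total ratio of 0.4 might seem to follow, but the SAP pairs that ratio with ALT above 3 x ULN, and nothing in the documents supports it as a stand-alone stopping threshold. The product label and Investigator's Brochure are not among the documents and may add monitoring advice. This is a low-cost improvement worth considering, not a flaw that undermines the trial.

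**What to change.** In Section 6.1.7.2, add a clause that the total bilirubin exemption does not cover a predominantly direct rise in a subject with cirrhosis.

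Add a short paragraph for subjects with cirrhosis that applies regardless of ALT:

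- **Trigger:** a predominantly direct rise (for example total bilirubin at least 2 x ULN and above baseline, with the direct-fraction cut-off set by the sponsor's hepatology lead), or clinical signs of decompensation.
- **Action:** a prompt repeat, for example within one week as in Section 6.1.7.5, of ALT, AST, fractionated bilirubin, alkaline phosphatase and INR, together with an evaluation for decompensation.
- **Decision:** discontinue study drugs if decompensation is present. If only the direct rise is confirmed, decide on interruption with the medical director.

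The SAP needs no change and no scheduled test is added. The costs are a few extra blood draws and, rarely, an early stop that may be classed as SVR12 non-response under SAP Section 10.1.
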